1.3. Rationale for This Study

Over the last decade, changes in RA treatment strategies, accompanied by advances in drug development and the addition of targeted biological therapies, have greatly improved the outcomes for subjects with RA. Despite these developments, therapeutic challenges remain. The current conventional and biologic DMARDs may be ineffective or produce only partial responses in some subjects and may be associated with significant safety and tolerability concerns. There is a medical need for simple, orally administered therapies with novel and targeted mechanisms of action that can effectively improve the disease course while being safe and well-tolerated. MTX-naïve patients with RA have several medications to choose from, however, it is clear that as patients progress through the available therapies, they may be left with active disease and a need for additional options. Development of another drug for these patients is appropriate, since participation in this study will not preclude the use of approved RA therapies for these subjects in the future. Moreover, all subjects in this study will receive active drug: MTX, filgotinib, or a combination of the two, as well as frequent monitoring of their health and RA status. Any subjects considered to be non-responders at Week 24 and those with loss of response at 2 consecutive visits after week 30, will discontinue study drug and take standard of care medications.

Filgotinib is an orally administered, small molecule inhibitor of JAK1, an intracellular tyrosine kinase that is dysregulated in subjects with inflammatory disorders, including RA. Filgotinib has demonstrated clinical activity and a favorable safety and tolerability profile in Phase 2 studies in subjects with moderately to severely active RA.

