**Figure 1-1. Study Design**

At Week 24, subjects who have not achieved at least 20% improvement from Day 1 in both swollen joint count (SJC) and tender joint count (TJC) will discontinue investigational study drug dosing but will continue with study visits and assessments per protocol. All subjects meeting this criterion who discontinue from investigational therapy are to receive standard of care treatment for their RA as determined by the investigator.

All subjects who attain responder status at Week 24 will continue on their assigned study drug, in a blinded fashion through Week 52. Placebo-responders at Week 24 will continue on placebo in a blinded fashion through Week 52.

All subjects who have received at least one dose of study drug and exit the study early will complete an early termination (ET) visit at the time of study discontinuation, with a follow up visit four weeks after the last dose of study drug (Post Treatment visit Week 4), regardless of dosing duration.

At completion of the 52-week dosing period all subjects (who did not discontinue assigned study drug or have not met criteria for loss of therapeutic response) will be provided the option to enroll into a separate Long Term Extension (LTE) study (GS-US-417-0304).

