### 3.3. Strata and Covariates

Subjects will be randomly assigned to treatment groups via the interactive web response system (IWRS) in a 2:1:1:2 ratio to filgotinib 200mg + MTX, filgotinib 100mg + MTX, filgotinib 200mg, and MTX using a stratified randomization schedule. Stratification will be based on the following variables:

- Geographic region (**Group A** includes the following countries: Australia, Belgium, Canada, France, Germany, Ireland, Israel, Italy, Netherlands, New Zealand, Republic of Korea, Singapore, South Africa, Spain, Sweden, Switzerland, United Kingdom, and USA; **Group B** includes the following countries: Bulgaria, Croatia, Czech Republic, Estonia, Georgia, Hungary, India, Latvia, Moldova, Poland, Romania, Russia, Serbia, Slovakia, and Ukraine; **Group C** includes the following countries: Argentina, Brazil, Chile, Colombia, Mexico, Peru, and Puerto Rico; **Group E** includes Japan; **Group D** includes the following countries/regions China (was originally planned but no subjects were screened or enrolled from this region), Hong Kong, Malaysia, Philippines, Taiwan, Thailand, and Vietnam.
- Presence of RF or anti-CCP Ab (Yes or No) (Presence of RF = No if RF < 15 IU/mL; Presence of anti-CCP Ab = No if anti-CCP Quant < 17 U/mL)

If there are discrepancies in stratification factor values between the IWRS and the clinical database, the values recorded in the clinical database will be used for analyses.

For efficacy endpoints, stratification factors and the baseline value of the efficacy variable(s) will be included as covariates in the efficacy analysis model, as specified in Section 6.

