The change from baseline in FACIT-Fatigue scale score at each postbaseline visit through Week 52 will be analyzed using similar MMRM models as for SF-36. To test for a treatment difference between each filgotinib dose group and placebo, LS mean difference along with 95% CI and p-values will be presented for each postbaseline visit. Missing change scores due to missing study visits or early withdrawal will not be otherwise imputed using the MMRM approach. Summary statistics of the actual score and change from baseline in FACIT-Fatigue scale score will also be displayed by treatment and visit.

- **EQ-5D-5L**

Summary statistics of two outcomes of the EQ-5D-5L described as the following will be provided:

- A health profile: the number and percentage of subjects at each categorical response for the 5 dimensions (mobility, self-care, usual activity, pain/discomfort, and anxiety/depression) will be provided by treatment and visit.
- A self-perceived current health score: calculated from patient level EQ VAS responses (continuous variable). Descriptive statistics (sample size, mean, SD, min, median, and max) will be provided by treatment and visit.

The change from baseline in EQ VAS score through Week 52 will be analyzed using similar MMRM models as for SF-36. To test for a treatment difference between each filgotinib dose group and placebo, LS mean difference, 95% CI and p-values will be presented. Missing change scores due to missing study visits or early withdrawal will not be otherwise imputed using the MMRM approach.

- **WPAI – RA**

Summary statistics of the actual scores and change from baseline in each of the four types of scores of WPAI-RA (absenteeism, presenteeism, work productivity loss, and activity impairment) will be summarized by treatment and visit using descriptive statistics (sample size, mean, SD, median, Q1, Q3, minimum and maximum).

The analyses of absenteeism, presenteeism, and work productivity loss will be based on subjects employed at both baseline and postbaseline visits.

- **HRUQ**

Summary statistics will be provided for all the following parameters by treatment group and visit.

*Healthcare resource utilization – Outpatient visits:*

— Number and percentage of subjects with any medical visits, and the number of visits related to RA will be provided for the categories:

- Outpatient Healthcare Provider
- Emergency Room
- Chiropractor, Physical or Occupational Therapist

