## Appendix 6. SAS Programming for Tipping Point Analysis for Binary Endpoint

The following **%tp\_binary** macro generates multiple imputed data and a set of the shift parameters that adjust the imputed values will be examined.

```

/*-----*/
/*--- Delta-Adjustment Method for Tipping Point Analysis for Binary Endpoint ---*/
/*---
/*--- Generate imputed data set for specified shift parameters ---*/
/*--- data= input data set ---*/
/*--- smin= min shift parameter for active drug ---*/
/*--- smax= max shift parameter for active drug ---*/
/*--- sinc= increment of the shift parameter for active drug ---*/
/*--- pmin= min shift parameter for placebo drug ---*/
/*--- pmax= max shift parameter for placebo drug ---*/
/*--- pinc= increment of the shift parameter for placebo drug ---*/
/*--- trt= treatment group indicator ---*/
/*--- out= output imputed data set ---*/
/*-----*/

%macro tp_binary( data=, smin=, smax=, sinc=, pmin=, pmax=, pinc=, trt=, out=);
  data &out;
  set _null_ ;
  run;

  %let ncase_pbo = %sysevalf( (&pmax-&pmin)/&pinc, ceil );

  %do pc=0 %to &ncase_pbo;

    %let pj= %sysevalf( &pmin + &pc * &pinc);

    /*----- # of shift values -----*/
    %let ncase= %sysevalf( (&smax-&smin)/&sinc, ceil );

    /*----- Imputed data for each shift -----*/
    %do jc=0 %to &ncase;

      %let sj= %sysevalf( &smin + &jc * &sinc);

      proc mi data=&data seed=14823 nimpute=20 out=outmi;
        var trt01pn strat1V strat2V strat3V das28n;
        class trt01pn strat1V strat2V strat3V das28n;
        monotone logistic (das28n / link=glogit);
        mnar adjust( das28n(event='1') / adjustobs=(trt01pn="&trt") shift= &sj)
          adjust( das28n(event='1') / adjustobs=(trt01pn='3') shift= &pj);

      run;

      data outmi;
        set outmi;
        Shift Trt= &sj;
        Shift_Pbo= &pj;

      run;

```

```
data &out;  
    set &out outmi;  
run;  
%end;  
%end;  
%mend tp_binary;
```

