## Appendix 7. SAS Programming for Tipping Point Analysis for Continuous Endpoint

The following %tp\_conti macro generates multiple imputed data sets and a set of the shift parameters that adjust the imputed values will be examined.

```
*****  
/*--- Modified Tipping Point Analysis from Yuan's method ---*/  
/*---  
/*--- Generate imputed data set for specified shift parameters ---*/  
/*--- data= input data set ---*/  
/*--- smin= min shift parameter for active drug ---*/  
/*--- smax= max shift parameter for active drug ---*/  
/*--- sinc= increment of the shift parameter for active drug ---*/  
/*--- pmin= min shift parameter for placebo drug ---*/  
/*--- pmax= max shift parameter for placebo drug ---*/  
/*--- pinc= increment of the shift parameter for placebo drug ---*/  
/*--- trt= treatment group indicator (eg, 1= filgotinib 200 mg) ---*/  
/*--- out= output imputed data set ---*/  
*****
```

```
%macro tp_conti( data=, smin=, smax=, sinc=, pmin=, pmax=, pinc=, trt=, out=);  
  data &out;  
  set _null_ ;  
  run;
```

```
  %let ncase_pbo = %sysevalf( (&pmax-&pmin)/&pinc, ceil );
```

```
  %do pc=0 %to &ncase_pbo;
```

```
    %let pj= %sysevalf( &pmin + &pc * &pinc);
```

```
    /*----- # of shift values -----*/  
    %let ncase= %sysevalf( (&smax-&smin)/&sinc, ceil );
```

```
    /*----- Imputed data for each shift -----*/  
    %do jc=0 %to &ncase;
```

```
      %let sj= %sysevalf( &smin + &jc * &sinc);
```

```
      proc mi data=&data out=all_mono nimpute=15 seed=123;  
        var v_1 v_2 v_3 v_4 v_5 v_6 v_7 v_8 v_9;  
        mcmc chain=multiple impute=monotone;  
      run;
```

```
      proc sort data=all_mono; by _Imputation_ trt01pn; run;
```

```
      proc mi data=all_mono out=outmi seed=465 nimpute=1;  
        by _Imputation_ ;  
        var trt01pn strat1V strat2V strat3V v_1 v_2 v_3 v_4 v_5 v_6 v_7 v_8 v_9;  
        class trt01pn strat1V strat2V strat3V;  
        monotone regression;  
        mnar adjust( v_5 / adjustobs=(trt01pn="&trt") shift=&sj)  
          adjust( v_5 / adjustobs=(trt01pn='3') shift= &pj);
```

```
run;

data outmi;
    set outmi;
    Shift_Trtr= &sj;
    Shift_Pbo= &pj;
run;

data &out;
    set &out outmi;
run;
%end;
%mend tp_conti;
```

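### Both printed tipping-point macros shift a hard-coded placebo arm that this trial does not have; with arm codes undefined, the SAP does not show that the MTX-alone comparator is ever shifted

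*SAP*

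**What the plan says.** **Design.** SAP 3.3 randomizes subjects "in a 2:1:1:2 ratio to filgotinib 200mg + MTX, filgotinib 100mg + MTX, filgotinib 200mg, and MTX using a stratified randomization schedule". Protocol 1.3 states that "all subjects in this study will receive active drug: MTX, filgotinib, or a combination of the two". Protocol 3.3 and SAP 1.2 list the arms in the same order: filgotinib 200 mg alone third, MTX alone fourth.

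**What the tipping-point analysis must do.** SAP 6.2.4.2 asks how missing data affect the ACR20 comparison of each filgotinib group with MTX alone. SAP 6.3.3.2 requires missing values for the continuous endpoints to be varied independently by treatment group until the conclusion reverses.

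**What the printed code does.** Each macro has one shift for the active arm, chosen by the argument `&trt`, and a second described as "pmin= min shift parameter for placebo drug" (with matching maximum and increment). In both macros the second shift is applied by "adjustobs=(trt01pn='3') shift= &pj". No argument identifies the comparator. The only arm code the documents give is an example in Appendix 7: "trt= treatment group indicator (eg, 1= filgotinib 200 mg". Two arms receive 200 mg, so even that does not identify one arm.

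**Placebo wording elsewhere.** For FACIT-Fatigue and EQ VAS, SAP 6.4.2 opens the model comparison with "To test for a treatment difference between each filgotinib dose group and placebo". SAP 1.2, under the design figure, says "Placebo-responders at Week 24 will continue on placebo in a blinded fashion through Week 52".

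**The concern.** The code appears to have been written for a different, placebo-controlled design and not adapted. A tipping-point analysis is informative only if it can shift both arms of the comparison. For a superiority claim the unfavourable scenario has two parts: missing subjects on filgotinib do worse than imputed, and missing subjects on MTX alone do better. If the second shift goes to an arm outside the comparison, only the first part is tested and the result can look sturdier than it is.

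These are the only analyses in the SAP that drop the missing-at-random assumption and search for a reversal. They cover the primary endpoint and all key secondary endpoints. As printed, a reader cannot tell which arm the second shift moves.

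**Working it through.** **1. The plan's own figures.** SAP 1.3 assumes ACR20 rates of 62% on MTX alone and 78% on filgotinib, with 400 subjects in each of the two main arms. Recomputed power for that difference is 99.9% (400 vs 400) and 98.3% (400 vs 200), consistent with the stated figure of over 90%. The mTSS calculation (difference 0.62, SD 2.7, 90% power) gives 399 per arm against the stated 400. Neither is in dispute.

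**2. Which arms are shifted.** Number the arms in listed order: 1 = filgotinib 200 mg + MTX, 2 = filgotinib 100 mg + MTX, 3 = filgotinib 200 mg alone, 4 = MTX alone.

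| `&trt` (active arm tested) | Codes shifted | MTX alone (4) shifted? |
|---|---|---|
| 1 | 1 and 3 | no |
| 2 | 2 and 3 | no |
| 3 | 3 only; both adjustments aim at it | no |

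If the data set instead codes MTX alone as 3, the second shift does reach the comparator.

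**3. Other signs that the code is not adapted.**
- It uses `strat1V` to `strat3V`; SAP 3.3 has two factors (region, and RF or anti-CCP status).
- The binary macro handles only `das28n`, so it has no ACR20 outcome.
- The continuous macro shifts `v_5` of nine variables. For HAQ-DI the visits run Baseline, Weeks 2, 4, 8, 12, 16, 20, 24, 30. So `v_5` is Week 12 if `v_1` is Baseline, or Week 16 if `v_1` is Week 2, but not Week 24. mTSS has three time points in all. SF-36 and FACIT-Fatigue have six. The `v_` coding is undefined too.
- For DAS28(CRP), the multiple-imputation text in SAP 6.3.3.2 classifies subjects at 3.2 or below at Week 12; the endpoint is below 2.6 at Week 24.

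**4. What an unshifted comparator could hide.** Missingness is not given in the documents, so m is an assumption, equal in both arms. Take 400 vs 400 and a pooled two-proportion z-test as a simple stand-in for the planned logistic model. Treat 62% and 78% as the rates among observed subjects.
- Filgotinib, all missing set to non-responder: 0.78(1 − m)
- MTX, missing left as imputed: 0.62
- MTX, all missing set to responder: 0.62(1 − m) + m

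At m = 0.10 filgotinib is 0.702.
- MTX unshifted: difference 0.702 − 0.620 = 0.082; pooled 0.661; SE = √(0.661 × 0.339 × 2/400) = 0.0335; z = 2.45; p = 0.014.
- MTX shifted to 0.658: difference 0.044; pooled 0.680; SE = 0.0330; z = 1.33; p = 0.18.

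| m | p, filgotinib only shifted | p, both shifted |
|---|---|---|
| 5% | 0.0002 | 0.0018 |
| 8% | 0.0034 | 0.041 |
| 10% | 0.014 | 0.18 |
| 12% | 0.0485 | 0.53 |
| 15% | 0.20 | 0.67 |

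For a 200-subject filgotinib arm the pairs are 0.018 and 0.098 at 8%, and 0.0475 and 0.28 at 10%.

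**5. Sensitivity to the meaning of 62%.** The primary analysis counts missing as failure. If the planned rates already include that, the observed MTX rate at m = 0.12 is 0.62/0.88 = 0.705, filgotinib with all missing failed is 0.78, and MTX with all missing responding is 0.62 + 0.12 = 0.74. Then p = 0.015 (difference 0.0755, SE 0.0309) against 0.19 (difference 0.04, SE 0.0302). At m = 0.10 it is 0.0035 against 0.05. The band moves to higher missingness but does not vanish.

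**6. Does a shift on code 3 move the main comparison indirectly?** One simulated four-arm data set was analysed: planned rates, 10% missing, logistic imputation, 20 imputations, Rubin's rules, and a shift of −5 on the logit scale in arm 1. Raising the second shift from 0 to 5 on code 3 left the arm 1 vs MTX log odds ratio at 0.318 to 0.319 (p 0.042 to 0.041). The same shift on code 4 took it from 0.318 to 0.159 (p 0.042 to 0.31).

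**The case against.** - **The coding is unknown.** No text maps code 3 to an arm, and the one example given does not clearly match the first listed arm. This stands. A reader might infer that the MTX arm is never shifted and that every comparison will look too robust. The documents do not support that as a plain statement: it holds only if codes follow the listed order and `&trt` is used for the active arm, as the macro comments say.
- **The code must be rewritten before use anyway.** It has no ACR20 variable, and its visit variables do not fit mTSS, SF-36 or FACIT-Fatigue, so the ACR20 figures describe a macro not yet written. That is fair, and it is why they are only an illustration. It also shows that changing the 3 alone would not be enough.
- **The governing text is right.** SAP 6.2.4.2 and 6.3.3.2 name MTX alone and independent shifts. True, but the only code supplied names a placebo arm instead, so text and program must be reconciled.
- **The active-arm shift still works.** It does, and at 15% missing it tips the result by itself in the first table. In that grid (400 vs 400) the two approaches disagree at 10% and 12%, under extreme imputations.
- **The placebo wording in SAP 6.4.2 is recoverable.** Those models refer back to SF-36, which is compared with MTX alone; SAP 6.3.2 does the same for FACIT-Fatigue at Week 24; and the p-values under 6.4.2 are nominal. This stands; it is a wording correction.

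**Conclusion.** The concern holds in conditional form. Without any assumption, both macros name a comparator that does not exist, fix it to an undefined code, and use one stratification variable too many. If the codes follow the listed arm order, the MTX-alone arm is not shifted and a tipping point could be missed. The size depends on missingness, which the documents do not give. With 400 per arm and extreme imputations, the conclusion differs at about 10% to 12% missing if the planned rates are observed-case rates, and at somewhat higher missingness if they already count missing as failure. If MTX alone is coded 3, the comparator is shifted as intended and what remains is wrong labels, undefined codes and the other unadapted parts.

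The effect is confined to sensitivity analyses and wording. The primary test, the sample size and the other missing-data analyses of ACR20 (non-responder imputation, observed case, LOCF, multiple imputation) do not depend on these macros. The matter should be corrected before unblinding.

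**What to change.** In Appendices 6 and 7:
- Define `trt01pn` for all four arms.
- Replace the fixed 3 with a macro argument for the comparator, set to MTX alone, and relabel the placebo parameters.
- Use this trial's two stratification factors.
- Set the outcome and shifted visit for each endpoint at Week 24: ACR20 as well as DAS28(CRP) below 2.6, and the Week 24 variable instead of a fixed `v_5`, with the `v_` coding stated.

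In the SAP text:
- In 6.3.3.2, correct the DAS28(CRP) imputation step to below 2.6 at Week 24.
- In 6.4.2, name MTX alone as the comparator for FACIT-Fatigue and EQ VAS.
- Reconcile the placebo-responder sentence in 1.2 with the four-arm design.

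The cost is SAP wording and modest programming. No new data are needed and nothing changes for subjects.

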## Appendix 7. SAS Programming for Tipping Point Analysis for Continuous Endpoint

The following %tp\_conti macro generates multiple imputed data sets and a set of the shift parameters that adjust the imputed values will be examined.

```
*****  
/*--- Modified Tipping Point Analysis from Yuan's method ---*/  
/*---  
/*--- Generate imputed data set for specified shift parameters ---*/  
/*--- data= input data set ---*/  
/*--- smin= min shift parameter for active drug ---*/  
/*--- smax= max shift parameter for active drug ---*/  
/*--- sinc= increment of the shift parameter for active drug ---*/  
/*--- pmin= min shift parameter for placebo drug ---*/  
/*--- pmax= max shift parameter for placebo drug ---*/  
/*--- pinc= increment of the shift parameter for placebo drug ---*/  
/*--- trt= treatment group indicator (eg, 1= filgotinib 200 mg) ---*/  
/*--- out= output imputed data set ---*/  
*****
```

```
%macro tp_conti( data=, smin=, smax=, sinc=, pmin=, pmax=, pinc=, trt=, out=);  
  data &out;  
  set _null_ ;  
  run;
```

```
  %let ncase_pbo = %sysevalf( (&pmax-&pmin)/&pinc, ceil );
```

```
  %do pc=0 %to &ncase_pbo;
```

```
    %let pj= %sysevalf( &pmin + &pc * &pinc);
```

```
    /*----- # of shift values -----*/  
    %let ncase= %sysevalf( (&smax-&smin)/&sinc, ceil );
```

```
    /*----- Imputed data for each shift -----*/  
    %do jc=0 %to &ncase;
```

```
      %let sj= %sysevalf( &smin + &jc * &sinc);
```

```
      proc mi data=&data out=all_mono nimpute=15 seed=123;  
        var v_1 v_2 v_3 v_4 v_5 v_6 v_7 v_8 v_9;  
        mcmc chain=multiple impute=monotone;  
      run;
```

```
      proc sort data=all_mono; by _Imputation_ trt01pn; run;
```

```
      proc mi data=all_mono out=outmi seed=465 nimpute=1;  
        by _Imputation_ ;  
        var trt01pn strat1V strat2V strat3V v_1 v_2 v_3 v_4 v_5 v_6 v_7 v_8 v_9;  
        class trt01pn strat1V strat2V strat3V;  
        monotone regression;  
        mnar adjust( v_5 / adjustobs=(trt01pn="&trt") shift=&sj)  
          adjust( v_5 / adjustobs=(trt01pn='3') shift= &pj);
```

```
run;

data outmi;
    set outmi;
    Shift_Trtr= &sj;
    Shift_Pbo= &pj;
run;

data &out;
    set &out outmi;
run;
%end;
%mend tp_conti;
```
